5.3. Lifestyle Considerations

The following guidelines are provided:

5.3.1. Meals and Dietary Restrictions

- Participants must abstain from all food and drink (except water) at least 4 hours prior to any safety laboratory evaluations.
- While participants are confined, their total daily nutritional composition should be approximately 55% carbohydrate, 30% fat, and 15% protein. The daily caloric intake per participant should not exceed approximately 3200 kcal.

5.3.2. Caffeine, Alcohol, and Tobacco

- Participants will abstain from caffeine -containing products for 24 hours prior to the start of dosing and during confinement in the CRU.
- Participants will abstain from alcohol for 24 hours prior to admission to the CRU and continue abstaining from alcohol during confinement in the CRU. Participants may

undergo an alcohol breath test or blood alcohol test at the discretion of the investigator.

- Participants will abstain from the use of tobacco- or nicotine containing- products for 24 hours prior to dosing and during confinement in the CRU.

5.3.3. Activity

- Participants will abstain from strenuous exercise (eg, heavy lifting, weight training, calisthenics, aerobics) for at least 48 hours prior to each blood collection for clinical laboratory tests. Walking at a normal pace will be permitted.

5.3.4. Contraception

The investigator or his or her designee, in consultation with the participant, will confirm that the participant has selected an appropriate method of contraception for the individual participant and his or her partner(s) from the permitted list of contraception methods (see [Appendix 4 Section 10.4.4](#)) and will confirm that the participant has been instructed in its consistent and correct use. At time points indicated in the [SoA](#), the investigator or designee will inform the participant of the need to use highly effective contraception consistently and correctly and document the conversation and the participant's affirmation in the participant's chart (participants need to affirm their consistent and correct use of at least 1 of the selected methods of contraception). In addition, the investigator or designee will instruct the participant to call immediately if the selected contraception method is discontinued or if pregnancy is known or suspected in the participant or partner.

5.4. Screen Failures

Screen failures are defined as participants who consent to participate in the clinical study but are not subsequently randomly assigned to study intervention/enrolled in the study. A minimal set of screen failure information is required to ensure transparent reporting of screen failure participants to meet the CONSORT publishing requirements and to respond to queries from regulatory authorities. Minimal information includes demography, screen failure details, eligibility criteria, and any SAE.

Individuals who do not meet the criteria for participation in this study (screen failure) may be rescreened.

6. STUDY INTERVENTION

Study intervention is defined as any investigational intervention(s), marketed product(s), placebo, medical device(s), or study procedure(s) intended to be administered to a study participant according to the study protocol.

For the purposes of this protocol, study intervention refers to PF-06480605 and its placebo.

6.1. Study Intervention(s) Administered

For this study, the study interventions are PF-06480605 and its placebo.

PF-06480605 is a sterile solution for subcutaneous injection. PF-06480605 will be provided in dosage strength of 100 mg/mL in single-use, sterile vials. Each vial contains 200 mg of PF-06480605 in 2 mL of solution. Placebo for PF-06480605 will also be provided by Pfizer as a sterile liquid solution in single-use, sterile vials.

PF-06480605 and placebo are supplied in a 6 mL glass vial and a 2 mL extractable volume with a stopper and aluminum overseal. All vials will be provided in cartons and both will be labeled according to local regulatory requirements. The site will take all necessary precautions to maintain the investigator and site personnel blind.

6.1.1. Administration

Participants will receive study intervention at approximately 0800 hours (plus or minus 2 hours). Study medication does not require fasting, but it should be noted that the safety laboratory test at Day -1 prior to the study medication need a fast of at least 4 hours. Study medication will be administered subcutaneously. Injection should occur at a site on the abdomen. All participants will be administered one or more 1.5 mL SC injections. The number of SC injections depends on the doses such that one SC injection for 150 mg, and three SC injections for 450 mg. Thus, the number of SC injections will be maximal 3 times. Each injection is to occur at a different site on the abdomen, approximately 1 cm apart.

Administer study intervention according to the IP manual.

6.2. Preparation/Handling/Storage/Accountability

1. The investigator or designee must confirm appropriate temperature conditions have been maintained during transit for all study interventions received and any discrepancies are reported and resolved before use of the study intervention.
2. Only participants enrolled in the study may receive study intervention and only authorized site staff may supply or administer study intervention. All study interventions must be stored in a secure, environmentally controlled, and monitored (manual or automated recording) area in accordance with the labeled storage conditions with access limited to the investigator and authorized site staff. At a minimum, daily minimum and maximum temperatures for all site storage locations must be documented and available upon request. Data for nonworking days must indicate the minimum and maximum temperatures since previously documented for all site storage locations upon return to business.
3. Any excursions from the study intervention label storage conditions should be reported to Pfizer upon discovery along with any actions taken. The site should actively pursue options for returning the study intervention to the storage conditions described in the labeling, as soon as possible. Once an excursion is identified, the study intervention must be quarantined and not used until Pfizer provides permission to use the study intervention. Specific details regarding the definition of an excursion and information the site should report for each excursion will be provided to the site in the IP manual.

4. Any storage conditions stated in the SRSD will be superseded by the storage conditions stated on the product label.
5. Study interventions should be stored in their original containers and in accordance with the labels.
6. See the IP manual for storage conditions of the study intervention.
7. Deviations from the storage requirements, including any actions taken, must be documented and reported to Pfizer upon discovery. The site should actively pursue options for returning the study intervention to the storage conditions described in the labeling, as soon as possible. Once an excursion is identified, the study intervention must be quarantined and not used until Pfizer provides permission to use the study intervention. It will not be considered a protocol deviation if Pfizer approves the use of the study intervention after the temperature excursion. Use of the study intervention prior to Pfizer approval will be considered a protocol deviation. Specific details regarding the definition of an excursion and information the site should report for each excursion will be provided to the site in the IP manual.
8. The sponsor or designee will provide guidance on the destruction of unused study intervention (eg, at the site). If destruction is authorized to take place at the investigator site, the investigator must ensure that the materials are destroyed in compliance with applicable environmental regulations, institutional policy, and any special instructions provided by Pfizer, and all destruction must be adequately documented.
9. The investigator, institution, or the head of the medical institution (where applicable) is responsible for study intervention accountability, reconciliation, and record maintenance (ie, receipt, reconciliation, and final disposition records), such as the IPAL or sponsor-approved equivalent. All study interventions will be accounted for using a study intervention accountability form/record.
10. Further guidance and information for the final disposition of unused study interventions are provided in the PCRU's local/site procedures. All destruction must be adequately documented. If destruction is authorized to take place at the investigator site, the investigator must ensure that the materials are destroyed in compliance with applicable environmental regulations, institutional policy, and any special instructions provided by Pfizer.

Upon identification of a product complaint, notify the sponsor within 1 business day of discovery.

6.2.1. Preparation and Dispensing

Within this protocol, preparation refers to the investigator site activities performed to make the study intervention ready for administration or dispensing to the participant by qualified staff. Dispensing is defined as the provision of study intervention, concomitant treatments,

and accompanying information by qualified staff member(s) to a healthcare provider, participant in accordance with this protocol. Local health authority regulations or investigator site guidelines may use alternative terms for these activities.

PF06480605 and placebo will be prepared and dispensed by qualified unblinded site personnel according to the IP manual. The study intervention will be administered by unblinded administrator to the participant.

6.3. Measures to Minimize Bias: Randomization and Blinding

6.3.1. Allocation to Study Intervention

Participants will be randomly assigned to receive study intervention from a central randomization scheme. Investigators will remain blinded to each participant's assigned study intervention throughout the course of the study. In order to maintain this blind, an otherwise uninvolved third party (for example, pharmacist) will be responsible for the preparation and dispensing of all study intervention according to the randomization schedule and assigned treatment for the individual participant.

6.3.2. Breaking the Blind

The method for breaking the blind in this study will be manual. A sealed envelope that contains the study intervention assignment(s) for each participant will be provided to the investigator. The sealed envelope will be retained by the investigator (or representative) in a secured area. In case of an emergency, the investigator has the sole responsibility for determining if unblinding of a participant's treatment assignment is warranted. Participant safety must always be the first consideration in making such a determination. If the investigator decides that unblinding is warranted, the investigator should make every effort to contact the sponsor prior to unblinding a participant's treatment assignment unless this could delay further management of the participant. If a participant's treatment assignment is unblinded, the sponsor must be notified within 24 hours after breaking the blind. When the blinding code is broken, the reason must be fully documented and entered on the CRF/DCT.

Once the study is complete, all envelopes (sealed and opened) must be inventoried and retained until authorization for destruction has been provided.

Blinding codes should be broken only in exceptional circumstances when knowledge of the actual treatment code is absolutely essential for further management of the participant. Investigators are encouraged to discuss with a member of the study team if they believe that unblinding is necessary. When the blinding code is broken, the reason must be fully documented and entered on the CRF/DCT.

This is an investigator- and participant-blind (Sponsor open) placebo-controlled study. Blood specimens will be obtained from all participants for PK analysis to maintain the study blind at the investigator site. The investigator site staff with the exception of the site pharmacist(s), pharmacy assistant(s) and study drug administrator(s) and blinded study monitor, if assigned, will be blinded to study treatment. Other Pfizer personnel will be unblinded to participant treatments in order to permit real-time interpretation of the safety and PK data; and provide

information necessary to potentially alter the dose escalation sequence. The blinded study monitor, if assigned, will remain blinded to treatment until all monitoring for the study has been completed. Specimens from participants randomized to placebo will not be routinely analyzed. To minimize the potential for bias, treatment randomization information will be kept confidential by Pfizer unblinded personnel and will not be released to the blinded investigator or blinded investigator site personnel until the study database has been locked or the investigator requests unblinding for safety reasons.

6.4. Study Intervention Compliance

The study intervention will be administered by investigator site personnel. Deviation(s) from the prescribed dosage regimen should be recorded in the CRF.

The site will complete the required dosage Preparation Record located in the IP manual. The use of the Preparation Record is preferred, but it does not preclude the use of an existing appropriate clinical site documentation system. The existing clinical site's documentation system should capture all pertinent/required information on the preparation and administration of the dose. This may be used in place of the Preparation Record after approval from the sponsor and/or designee.

6.5. Concomitant Therapy

Use of prescription or nonprescription drugs and dietary and herbal supplements are prohibited within 7 days or 5 half-lives (whichever is longer) prior to the first dose of study intervention. Recent exposure to live vaccines within 28 days of the screening visit is prohibited. Limited use of nonprescription medications that are not believed to affect participant safety or the overall results of the study may be permitted on a case-by-case basis following approval by the sponsor. Acetaminophen/paracetamol may be used at doses of ≤ 1 g/day. All concomitant treatments taken during the study must be recorded with indication, daily dose, and start and stop dates of administration. All participants will be questioned about concomitant treatment at each clinic visit.

Treatments taken within 28 days before the first dose of study intervention will be documented as a prior treatment. Treatments taken after the first dose of study intervention will be documented as concomitant treatments.

6.6. Dose Modification

Dose modification is not allowed in the current study.

6.7. Intervention After the End of the Study

No intervention will be provided to study participants at the end of the study.

7. DISCONTINUATION OF STUDY INTERVENTION AND PARTICIPANT DISCONTINUATION/WITHDRAWAL

7.1. Discontinuation of Study Intervention

In rare instances, it may be necessary for a participant to permanently discontinue study intervention (definitive discontinuation). Reasons for definitive discontinuation of study intervention include the following as outlined in [Section 7.2](#).

If study intervention is definitively discontinued, the participant will remain in the study to be evaluated for PF-06480605. See the [SoA](#) for data to be collected at the time of discontinuation of study intervention.

See the [SoA](#) for data to be collected at the time of discontinuation of study intervention and follow-up for any further evaluations that need to be completed.

Potential Cases of Acute Kidney Injury

Abnormal values in SCr concurrent with presence or absence of increase in BUN that meet the criteria below, in the absence of other causes of kidney injury, are considered potential cases of acute kidney injury and should be considered important medical events.

An increase of ≥ 0.3 mg/dL (or ≥ 26.5 μ mol/L) in SCr level relative to the participant's own baseline measurement should trigger another assessment of SCr as soon as practically feasible, preferably within 48 hours from awareness.

If the second assessment (after the first observations of ≥ 0.3 mg/dL [or ≥ 26.5 μ mol/L] in SCr relative to the participant's own baseline measurement) is ≥ 0.4 mg/dL (or ≥ 35.4 μ mol/L), the participant should be discontinued from the study and adequate, immediate, supportive measures taken to correct apparent acute kidney injury.

Participants should return to the investigator site and be evaluated as soon as possible, preferably within 48 hours from awareness of the second assessment confirming abnormal SCr result. This evaluation should include laboratory tests, detailed history, and physical assessment. In addition to repeating SCr, laboratory tests should include serum BUN, serum creatine kinase, and serum electrolytes (including at a minimum potassium, sodium, phosphate/phosphorus, and calcium), in addition to urinary dipstick, urine microscopic examination, and urinary indices. All cases confirmed on repeat testing as meeting the laboratory criteria for acute kidney injury, with no other cause(s) of laboratory abnormalities identified, should be considered potential cases of drug-induced kidney injury irrespective of availability of all the results of the investigations performed to determine etiology of the abnormal SCr. If ≥ 2 healthy participants are noted to have 2 consecutive SCr results of ≥ 0.3 mg/dL (or ≥ 26.5 μ mol/L), an assessment of whether the finding may be considered an adverse drug reaction should be undertaken.

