2.2.2.2. Immunogenicity

2.2.2.2.1. B7541001

The incidence of ADA ranged from 50% to 100% for SAD and MAD cohorts. In participants receiving PF-06480605, 56 participants out of 68 participants were considered to be positive for ADA. The overall confirmed treatment induced incidence rate was 82.4%; however, there were 11 participants for whom PF-06480605 concentrations remained above the assay tolerance level throughout the study. For drug tolerance, the assay has the potential to report a false negative at drug concentrations higher than the stated amount, which may result in the inconclusive ADA results. Positive ADA samples were detected as early as 336 hours (14 days) post-dose in the SAD cohorts and on Day 29 in the MAD cohorts.

The incidence of NAb ranged from 0% for 2 SAD and 2 MAD cohorts to 100% for the 3 mg IV cohort. In participants receiving PF-06480605, 24 participants out of 68 participants were considered positive for NAb. The overall confirmed NAb incidence rate was 35.3%; however, there were 43 participants for whom PF-06480605 concentrations remained above the assay tolerance level throughout the study. Positive NAb samples were detected as early as 672 hours (28 days) post-dose in the SAD cohorts and 1680 hours (70 days) post-dose in the MAD cohorts. Where data were available, mean serum PF-06480605 concentrations were lower in participants identified as ADA positive, compared to participants identified as ADA not-positive, and were even lower in participants with NAb log titer ≥ 0.70 . Differences in mean serum PK parameters, namely exposure, between participants identified as ADA positive and ADA not-positive as well as between participants with NAb log titer <0.70 and ≥ 0.70 were more apparent for participants in MAD cohorts but no direct conclusions were able to be drawn from the data.

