2.2.2.3. Pharmacokinetics

2.2.2.3.1. B7541001

Following single IV infusion dosing of PF-06480605 under fasted conditions at doses ranging between 1 mg to 800 mg, the C_{max} was observed around 1.5 to 2 hours after the end of a 1-hour infusion followed by a multiphasic decline of serum concentrations over time, with mean $t_{1/2}$ values ranging between 6 to 23 days. Mean $t_{1/2}$ values at the lower doses appeared to be shorter than those observed at the higher doses which may be due in part to sensitivity of the assay (more quantifiable serum concentrations above the limit of quantification at later time points for the higher doses) and in part of CL values which were appeared to decrease with increasing doses.

Overall, PF-06480605 AUC increased in a greater than dose proportional manner across the 1 mg to 800 mg dose range, while C_{max} appeared to increase in an approximately dose proportional manner across the dose range studied.

Geometric mean PF-06480605 CL values appeared to decrease with increasing doses, with a mean estimate of 0.0180 L/hr at the 1 mg dose and 0.00688 L/hr at the 800 mg dose. V_{ss} was low, indicating that drug is localized mainly to the vascular compartment with mean values ranging between 3.4 to 5.5 L across all doses.

Following multiple SC dose administration of PF-06480605 at 30-mg, 100-mg, and 300-mg doses Q2W for a total of 3 doses, absorption from the site of injection was variable, with peak serum concentrations achieved within a median time at which T_{max} of 96 to 216 hours post-dose on Day 1, 192 to 335 hours post-dose on Day 15, and 48 hours post-dose on Day 29.

Dose normalized PK exposure (as measured by geometric mean AUC from time 0 to time τ , the dosing interval $[AUC_\tau]$ and C_{max}) on Day 1 indicated that following SC administration, exposure increased in a dose proportional manner with an increase in dose, while exposure on Days 15 and 29 trended toward greater than dose proportional increases across the 30 mg to 300 mg SC doses.

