7.2. Participant Discontinuation/Withdrawal From the Study

A participant may withdraw from the study at any time at his/her own request. Reasons for discontinuation from the study include the following:

- Refused further follow-up;
- Lost to follow-up;
- Death;
- Study terminated by sponsor;

At the time of discontinuing from the study, if possible, an early discontinuation visit should be conducted. See the [SoA](#) for assessments to be collected at the time of study discontinuation and follow up- and for any further evaluations that need to be completed.

The early discontinuation visit applies only to participants who are enrolled/randomized and then are prematurely withdrawn from the study. Participants should be questioned regarding their reason for withdrawal.

The participant will be permanently discontinued both from the study intervention and from the study at that time.

If a participant withdraws from the study, he/she may request destruction of any remaining samples taken and not tested, and the investigator must document any such requests in the site study records and notify the sponsor accordingly.

If the participant withdraws from the study and also withdraws consent (see Section 7.2.1 for disclosure of future information, no further evaluations should be performed and no additional data should be collected. The sponsor may retain and continue to use any data collected before such withdrawal of consent.

Lack of completion of all or any of the withdrawal/ET procedures will not be viewed as protocol deviations so long as the participant's safety was preserved.

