7.2.1. Withdrawal of Consent

Participants who request to discontinue receipt of study intervention will remain in the study and must continue to be followed for protocol -specified follow -up procedures. The only exception to this is when a participant specifically withdraws consent for any further contact with him or her or persons previously authorized by the participant to provide this information. Participants should notify the investigator in writing of the decision to withdraw consent from future follow-up, whenever possible. The withdrawal of consent should be explained in detail in the medical records by the investigator, as to whether the withdrawal is only from further receipt of study intervention or also from study procedures and/or posttreatment study follow -up, and entered on the appropriate CRF page. In the event that vital status (whether the participant is alive or dead) is being measured, publicly available

information should be used to determine vital status only as appropriately directed in accordance with local law.

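### In this single-dose study the kidney-injury rule ends scheduled follow-up without stopping any treatment, and its creatinine retest cut-offs omit the words that make them increases from baseline

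*Protocol*

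**What the plan says.** Protocol 7.1 deals with stopping study intervention. Its general rule is that after definitive discontinuation "the participant will remain in the study to be evaluated for PF-06480605".

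The kidney-injury paragraph in the same section has three steps.

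- A creatinine rise of at least 0.3 mg/dL (26.5 μmol/L) from the participant's own baseline prompts a retest, preferably within 48 hours.
- If the retest is at least 0.4 mg/dL (35.4 μmol/L), "the participant should be discontinued from the study and adequate, immediate, supportive measures taken to correct apparent acute kidney injury". A return visit for work-up follows, again preferably within 48 hours.
- A signal rule asks for an assessment of a possible adverse drug reaction if two or more "healthy participants are noted to have 2 consecutive SCr results of" 0.3 mg/dL or higher.

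Protocol 7.2 makes discontinuation from the study permanent. Its list opens with "Reasons for discontinuation from the study include the following" and names refusal, loss to follow-up, death and sponsor termination. On what is still collected it says: "At the time of discontinuing from the study, if possible, an early discontinuation visit should be conducted".

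The study gives a single dose (Protocol 4.1) and allows no dose modification (6.6).

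**The concern.** There are two separate problems.

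**The action.** When a postdose creatinine rise is found, the only dose has already been given. Leaving the study cannot reduce exposure; it can only end planned observation. The participant with a suspected drug reaction would become the one whose exposure, antibody response and scheduled safety course are least well described. This sits badly with the general rule in the same section. AUCinf and t1/2 are primary endpoints and depend on the later visits. Late antibody results matter too: in the earlier Western study, "Positive NAb samples were detected as early as 672 hours (28 days) post-dose in the SAD cohorts".

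**The cut-off.** The first trigger is explicitly a change from baseline. In the retest sentence the baseline phrase sits inside the parenthesis that describes the first observation, and the retest result itself is simply compared with 0.4 mg/dL. The signal rule has no baseline reference at all. Taken at their words, both are absolute values that an ordinary creatinine exceeds, so the retest would confirm nothing.

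**Working it through.** **1. The plan's own figures.** With an assumed factor of 88.4 μmol/L per mg/dL, 0.3 × 88.4 = 26.5 and 0.4 × 88.4 = 35.4. The unit conversions are right; the fault is the missing reference to baseline.

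**2. Literal and intended cut-offs.** Let b be baseline creatinine in mg/dL. The documents give no range; assume 0.5 to 1.1.

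- Intended: the retest must reach b + 0.4, that is 0.9 to 1.5.
- Literal: the retest must reach 0.4. The first trigger already puts creatinine at b + 0.3, which is at least 0.4 for any b ≥ 0.1. A retest fully back at baseline still qualifies for any b ≥ 0.4, so everyone in the assumed range would be removed after a transient rise.
- Signal rule, literal: two consecutive results of at least 0.3 are met by every b in the assumed range without any rise.

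**3. Visits lost.** SAP 3.5.5 puts postdose safety laboratory tests on Days 2, 5, 10, 15, 57, 85 and 114/ET. The visit headers in Protocol 1.3 give follow-up on Days 10, 15, 29, 43, 57, 85 and 114/ET. A rise found on Day 15 therefore forfeits Days 29, 43, 57 and 85, with the 114/ET visit brought forward.

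**4. Share of AUC observed.** This is an illustration that assumes one compartment and first-order absorption. Inputs from Protocol 2.2.2.3.1 are a median SC Tmax "of 96 to 216 hours post-dose on Day 1" (4 to 9 days) and an SC half-life of 8.7 to 21 days. Formulas:

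- ke = ln 2 / t1/2, with ka solved from Tmax = ln(ka/ke) / (ka − ke)
- F(t) = [(1 − e^(−ke·t))/ke − (1 − e^(−ka·t))/ka] / (1/ke − 1/ka)

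For a Day 15 rise (14 days after dosing), a retest 48 hours later falls at 16 days, and an early-termination visit 48 hours after that at 18 days. Same-day results are assumed.

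- t1/2 21, Tmax 9 (ke 0.0330, ka 0.264): F(16) = (12.43 − 3.73) / (30.30 − 3.79) = 33%
- t1/2 8.7, Tmax 4 (ke 0.0797, ka 0.573): F(16) = (9.04 − 1.75) / (12.55 − 1.75) = 68%

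| Last sample (days after dosing) | AUCinf observed |
|---|---|
| 16 | 33%–68% |
| 18 | 37%–72% |
| 56 | 82%–99% |
| 113 (Day 114) | 97%–100% |

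The span from Tmax to the last sample is 7 days (16 − 9) to 14 days (18 − 4). That is 7/21 = 0.3 to 14/8.7 = 1.6 half-lives, a weak basis for t1/2.

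AUC14 days is complete for a Day 15 rise. For earlier rises, with the last sample at the retest or at the early-termination visit, the share of AUC14 days observed is:

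| Rise found | Last sample (days after dosing) | AUC14 days observed |
|---|---|---|
| Day 2 | 3–5 | 10%–37% |
| Day 5 | 6–8 | 31%–63% |
| Day 10 | 11–13 | 75%–95% |

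The ±3-day visit windows could recover one visit for a Day 5 or Day 10 rise. A rise found on Day 57 costs little.

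**5. How likely.** At an assumed 1% risk, the chance of at least one event among 9 active participants is 1 − 0.99^9 = 8.6%. A pessimistic bound takes 0 events among the 68 actively treated in B7541001 (assuming such a rise would have been reported). The one-sided 95% upper limit is 1 − 0.05^(1/68) = 4.3%, giving 1 − (1 − 0.043)^9 = 33%. Both cover a rise at any time; an early rise is less likely.

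**6. Headcount.** One loss takes a cohort from 12 to 11. Mandatory replacement starts at 10 or fewer Day 57 completers (Protocol 9.2), so it would not be triggered. If the loss is on active drug, 1 of 9 profiles (11%) is affected.

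**The case against.** The strongest reply is that ending research blood draws in a healthy volunteer with apparent kidney injury, who gains nothing from the study, is a defensible protective choice. A specific rule may also stand beside a general one, and the list of reasons in 7.2 is open. This has force. It is why the fix keeps an investigator exit, and why the point is a poor fit within 7.1 rather than a hard contradiction.

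The design also tolerates the loss. It plans for 11 evaluable per cohort. AUCinf and t1/2 are reported only as data permit, SAP 5.3.3 sets parameters that cannot be derived to missing, and the population PK model uses all available data. All of this stands. None of it supplies late antibody or scheduled safety results for the affected person.

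On the cut-off, the retest happens only after a rise from baseline, and the text goes on to speak of confirming an abnormal result. A sensible investigator would read an increase. That is granted, but a rule that removes a participant should not depend on inference.

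Three stronger readings are tempting, and the documents do not support them.

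- A reader might infer that only PK, sTL1A and ADA/NAb sampling stops. Scheduled safety laboratory tests, ECGs and vital signs stop as well. Nor is the participant left unmonitored: 7.1 requires the work-up, 8.2.5 repeats clinically significant laboratory tests, and 8.3.1 and 8.3.3 continue adverse-event follow-up.
- A reader might infer that someone without late samples would be counted as NAb-negative, diluting the incidence. The SAP says neither this nor the opposite; a rule against imputation does not turn missing into negative.
- A reader might infer a conflict with 7.2.1, where participants "will remain in the study and must continue to be followed". That passage covers people who ask to stop, not a withdrawal that the protocol directs.

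**Conclusion.** The point holds as a low-priority wording defect. The rule stops no treatment, ends all remaining scheduled assessments apart from a possible early-termination visit, and fits poorly with its own section. If the rise is found on Day 15, about 28% to 67% of AUCinf would be unobserved (100% minus the 33%–72% above), t1/2 would be poorly estimable, and late ADA/NAb results would be missing for 1 of 9 active participants. A rise on Day 2 or Day 5 would also cut into AUC14 days. The event is unlikely, and one loss leaves the planned 11 evaluable.

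Separately, the 0.4 mg/dL and 0.3 mg/dL criteria are miswritten as absolute values, although the context shows that increases were meant.

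The AUC shares rest on the one-compartment model, Tmax and half-life carried over from the earlier study, and the assumed 48-hour steps. The creatinine comparison rests on an assumed baseline range. No sample size or planned analysis is in error.

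**What to change.** Change three phrases in Protocol 7.1.

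1. Replace the instruction to discontinue the participant from the study with: *stays in scheduled safety, PK, sTL1A and ADA/NAb follow-up to Day 114, unless consent is withdrawn or the investigator judges further sampling clinically inappropriate*. Keep the supportive measures as they are.
2. State the retest criterion as *an increase of ≥0.4 mg/dL (≥35.4 μmol/L) from own baseline*.
3. State the signal rule as *2 consecutive increases of ≥0.3 mg/dL (≥26.5 μmol/L) from own baseline*.

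No visits, samples or participants are added, because the follow-up visits are already scheduled. The one downside is some further research blood draws in a participant with a suspected kidney reaction, which the investigator exit limits.
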